This study builds on a body of preliminary work speaking to HRVB's potential as an addendum to first-line SUD treatments. We will be using the 'Lief Smart Patch' device in this research (<https://getlief.com>). The Lief Smart Patch is a small, wearable, electrocardiogram (ECG)-based heart rate monitor that is attached to the body utilizing skin safe ECG electrodes. ECG technology is known to be safe and carries no substantial risk. The device monitors heart rate variability (HRV) as an index of autonomic nervous system arousal and can prompt the wearer to engage in brief bursts of HRVB practice via a connected smartphone app when stress is inferred. Wearers are also able to engage in regularly scheduled HRVB practice, and practice *ad libitum*. The Lief biofeedback device is being used in this study to deliver a clinical intervention and collect physiological data; the effectiveness of the device itself is not being tested.

2. Specific Aims and Objectives

The aim of this pilot study is to administer heart rate variability biofeedback (HRVB) to adults with substance use disorder who are receiving outpatient treatment as usual (TAU) and compare them to a control group receiving TAU only on intervention outcomes that include alcohol/drug use and negative affect. The study's specific aims are as follows:

[figure not shown]
- Aim 1:** Assess ambulatory HRVB's uptake by individuals with SUD in terms of practice time, and perceived barriers to uptake based on qualitative participant feedback (proof-of-concept)
- Aim 2:** Test effects of HRVB practice on affect and substance use
 - a.** Test day-level effects of HRVB practice on affective states and substance use
 - b.** Test the accumulative, person-level effects of scheduled daily HRVB practice vs. in-the-moment HRVB practice, vs. their interaction on substance use during the 8-week intervention period

We hypothesize that participants receiving HRVB + TAU will have a lower alcohol/drug use lapse rate and demonstrate greater reductions in negative affect compared to controls receiving TAU only.

3. General Description of Study Design

Design Overview

We will recruit 120 adults with substance use disorder (SUD) in their first year of a current SUD recovery attempt. Participants will be randomized using the SAS statistical program to either the experimental ($n= 70$) or control group ($n= 50$). We will also recruit 10 experimental group participants to participate in focus groups ($n= 5$ in each).

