6. STUDY PROCEDURES

On the study intake Zoom call, after providing informed consent (~10min), participants will complete a series of questionnaires via a secure REDCap link provided in the Zoom chat-box (~45min). Following this, participants will be guided through the process of installing the TigerAware ecological momentary assessment app on their smartphone and instructed how to use it (~5min). Finally, for experimental group participants, the researcher will provide the study rationale and give brief instruction in paced breathing (~30min). Immediately following the intake call, the experimenter will arrange for a Lief device to be mailed to the participant by Lief Therapeutics, which will come with instructions for setting up the device and downloading the accompanying smartphone app.

To maximize ecological validity in this study, the same HRVB phone coaching offered to regular Lief subscribers will be available to the experimental group participants. The Lief coaches are experts in HRVB and can help with any technical issues with the equipment or queries pertaining to the participant's HRVB practice. Coaches will reach out to study participants to schedule a 20-minute onboarding call when the Lief equipment is ordered. During the orientation call, the Lief coach will cover the following topics:

- Why HRV matters for your mental and physical health
- How Lief's HRV tracking and biofeedback training will help you achieve your health and wellness goals

- How to do a Downtime practice (a.k.a. HRV biofeedback exercise)
- Understanding how Lief's autodosing program works
- The coach's role: *"As your coach, I will support you as a sensemaker of your data to optimize your use of the Lief so we help you self-regulate your stress response more effectively"*
- Communication expectations: Mostly in the app chat box, I'll respond on weekdays. Schedule 20-minute calls every 2 weeks in the app so we can review your progress together.

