All research staff at the MGH Recovery Research Institute are fully trained in relevant ethical principles and procedures, including maintaining confidentiality, and are certified by Collaborative Institutional Training Initiative (CITI) to conduct research with human subjects. During the study, we will notify officials, as mandated by law, if a participant reports intentions to harm himself/herself or others, or reports child or elder abuse. Participants will be informed of these limits to confidentiality during the consenting process. Serious adverse events will be reported to the MGH Institutional Review Board immediately by telephone and by written report within 24 hours of our receipt of information regarding the event.

8. Benefits

A potential participant benefit for the experimental group is improved substance use and affective outcomes. A potential participant benefit for both the experimental and control groups may be increased awareness of personal patterns in affect through the conduct of ecological momentary assessment.

There are also considerable benefits to society associated with this study. Substance problems carry a tremendous emotional, medical, interpersonal, and societal cost. The knowledge gained in this study may lead to the adoption of a novel SUD treatment tool that bridges gaps in existing treatment approaches. The minimal risks associated with this research are reasonable given the potential benefits of this study.

9. Statistical Analysis

Because this is a pilot study with limited power to detect statistical significance, we will focus on interpreting effect sizes to inform a subsequent R01 trial. We note however, certain design strengths that will allow us to maximize statistical power. For instance, in our regression models, rather than just looking at main effects of group, we will also assess Heart Rate Variability Biofeedback (HRVB) practice time as a continuous measure with controls scored as 0. Additionally, power to test day-level associations is boosted by the repeated measures design with up to 84 repeated, momentary assessments per participant.

Please note that we use the term “day-level” below to denote effects at the level of individual ecological momentary assessment (EMA) surveys. From this perspective we have up to 84 repeated, momentary assessments of affect and substance use.

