Using multilevel models where days (L1) are nested within persons (L2), we will explore the effects of day-level HRVB practice earlier in the day (i.e., lagged) on subsequent day-level negative affect (**Model 1**), craving (**Model 2**), positive affect (**Model 3**), and substance use (yes/no; **Model 4**), while also testing whether HRVB decouples the anticipated relationship of day-level negative affect (**Model 5**) and craving on subsequent substance use (**Model 6**).

In models 1-3 (multilevel linear regression models), the dependent variables will be day-level negative affect scores, day-level craving scores, and day-level positive affect scores, with lagged day-level minutes of scheduled practice, and lagged in-the-moment HRVB practice (with controls' HRVB practice coded as 0), and their interaction term (lagged scheduled practice \times lagged in-the-moment practice) as the independent variables, controlling for age, sex, nicotine use (yes/no), medications known to affect the cardiovascular system (yes/no), and baseline past-month AOD use (percent days abstinent).

A priori, we anticipate that both greater daily scheduled HRVB practice and in-the-moment HRVB practice will predict lower subsequent day-level negative affect and craving, and that their interaction will indicate additive benefits of combining scheduled and in-the-moment practice. The relationship between positive affect and HRVB has not previously been explored, so we will treat this aspect of the analysis as exploratory. Our benchmark for preliminary demonstration of treatment benefit will be semi-partial R²'s for practice time of $\geq .10$ (medium effect size).

Models 1-3

Negative affect = day-level scheduled HRVB practice_{t-1} + day-level in-the-moment HRVB practice_{t-1} + [day-level scheduled HRVB practice_{t-1} * day-level in-the-moment HRVB practice_{t-1}] + age + sex + nicotine use + medications known to affect the cardiovascular system + baseline past-month AOD use + error

Craving = day-level scheduled HRVB practice_{t-1} + day-level in-the-moment HRVB practice_{t-1} + [day-level scheduled HRVB practice_{t-1} * day-level in-the-moment HRVB practice_{t-1}] + age + sex + nicotine use + medications

*known to affect the cardiovascular system + baseline past-month AOD use
+ error*

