Positive affect = *day-level scheduled HRVB practice_{t-1} + day-level in-the-moment HRVB practice_{t-1} + [day-level scheduled HRVB practice_{t-1} * day-level in-the-moment HRVB practice_{t-1}] + age + sex + nicotine use + medications known to affect the cardiovascular system + baseline past-month AOD use + error*

In Model 4 (multilevel logistic regression), the dependent variable will be day-level substance use (yes/no), with lagged day-level minutes of scheduled, and lagged day-level minutes of in-the-moment HRVB practice (with controls' HRVB practice coded as 0), and their interaction term (scheduled practice \times in-the-moment practice) as the independent variables, controlling age, sex, nicotine use (yes/no), medications known to affect the cardiovascular system (yes/no), and baseline past-month AOD use (percent days abstinent). We will also test this model with group as independent variable instead of HRVB practice.

In Models 5-6 (multilevel logistic regression), we will use a model building approach, where we will systematically increase model complexity in steps to sequentially examine hypotheses while maintaining a parsimonious model. Likelihood ratio tests will be used to examine the relative fit of nested models (i.e., the difference in -2 log-likelihood statistics between pairs of base and expanded models).

In Model 5, the dependent variable will be day-level substance use (yes/no), with combined lagged day-level scheduled and lagged in-the-moment HRVB practice (with controls' HRVB practice coded as 0), lagged day-level negative affect, and the lagged HRVB practice \times lagged negative affect interaction term as the independent variables, controlling for age, sex, nicotine use (yes/no), medications known to affect the cardiovascular system (yes/no), and baseline past-month AOD use (percent days abstinent). We will also test this model with group as independent variable instead of HRVB practice.

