With $N= 100$, and 42 days of EMA monitoring with 2 self-reports per day, the multilevel models exploring day-level relationships between HRVB practice, affect, and substance use will include 8,300 clustered observations. Given 5% alpha and a substance use/HRVB practice association of $r= 0.15$, and assuming conditional independence, we will have >99% power to predict a main effect of HRVB practice in Models 1-6.

Aim 2b. Test the accumulative, person-level effects of scheduled daily HRVB practice vs. in-the-moment HRVB practice, vs. their interaction on substance use during the 8-week intervention period

To begin to tease out the aggregated effects of scheduled vs. in-the-moment HRVB practice on substance use, we will run a linear regression model with percent days abstinent (PDA) from alcohol and other drugs (AOD) over the 8-week study period as the dependent variable, with total aggregated scheduled HRVB practice time, total aggregated in-the-moment HRVB practice time, and their interaction term (scheduled practice \times in-the-moment practice) as independent variables (with controls' HRVB practice coded as 0), controlling for age, sex, nicotine use (yes/no), medications known to affect the cardiovascular system (yes/no), and baseline past-month AOD use (percent days abstinent; **Model 7**). We will also run versions of this model testing a main effect of group, and number of in-the-moment practice sessions rather than aggregated in-the-moment HRVB practice time.

A priori, we anticipate that both greater accumulative scheduled HRVB practice, and accumulative in-the-moment HRVB practice will predict greater PDA, and importantly, that their interaction will indicate additional benefits of combining scheduled and in-the-moment practice. A semi-partial R^2 value for HRVB practice time $\geq .10$ (medium effect size) will be our benchmark for preliminary demonstration of aggregate-level treatment benefit.

An ancillary aim of this study is to explore the effects of differing HRVB practice times on treatment outcomes. We will conduct a post hoc regions-of-significance analysis to explore the moderation effect of practice time on the relationship between PDA and HRVB practice. This analysis will consider the effect for several alternate cutoff scores representing the 10th, 20th, 30th, 40th and 50th percentiles of practice time.

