Another ancillary aim is to garner a better understanding of when HRVB effects come on-board and how stable the effects are once established. To accomplish this, we will explore how the effect of HRVB on affective states and substance use vary over the trail using time-varying effects modeling (TVEM). TVEM estimates a non-parametric spline regression that flexibly estimates how the association between a predictor and outcome across continuous time (e.g., days). The series of regression coefficients produced by TVEM are presented graphically with 95% confidence intervals to demonstrate the magnitude and direction of the association between predictor and outcome across time. The P-spline technique, which automatically selects the best coefficient function through balancing tradeoffs between model fit and parsimony, will be used for all models.

Model #7

PDA = *total scheduled HRVB practice + total in-the-moment HRVB practice + [total scheduled HRVB practice * total in-the-moment HRVB practice] + age + sex + nicotine use + medications known to affect the cardiovascular system + baseline past-month AOD use + error*

Aim 2b Power

Though our emphasis will be on effect size interpretation rather than statistical significance, we note that with $N= 100$, 80% power, and a 5% alpha level, the detectable effect size is $R^2= .10$ (small effect size).

10. Monitoring and Quality Assurance

In an effort to meet the MGB policy for Data and Safety Monitoring, we have created a system for oversight of the project. Oversight of internal monitoring of the subjects' safety is conducted by the PI, [name].

On a weekly basis, the PI and study staff will discuss the progress of the study, review data quality, recruitment, study retention and examine other factors that may affect the outcomes. We will review the rate of adverse events to determine any changes in participant risk. The investigators are available to meet outside of the weekly meetings, if necessary, due to concerns regarding a particular participant or any problems that may arise for participants.

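### Practice models code every control as 0 and carry no arm term, so an arm effect that bypasses practice minutes can appear as a practice effect, chiefly in Model 7

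*Combined protocol and SAP*

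**What the plan says.** - **Coding.** The introduction to Section 9 lists among the features that help power: "we will also assess Heart Rate Variability Biofeedback (HRVB) practice time as a continuous measure with controls scored as 0". The same coding is repeated for the models under Aims 2a and 2b.
- **Models 1-3** (negative affect, craving, positive affect) contain lagged scheduled minutes, lagged in-the-moment minutes, their product and five covariates. Neither an arm term nor a group version is described.
- **Models 4-6** (substance use, multilevel logistic) each carry the sentence "We will also test this model with group as independent variable instead of HRVB practice". Here group replaces practice.
- **Model 7** (percent days abstinent) uses "total aggregated scheduled HRVB practice time, total aggregated in-the-moment HRVB practice time, and their interaction term". Its equation reads "total scheduled HRVB practice + total in-the-moment HRVB practice + [total scheduled HRVB practice * total in-the-moment HRVB practice] + age + sex" and continues with the remaining covariates; arm is not among them. The text adds "We will also run versions of this model testing a main effect of group", without saying whether the practice terms stay in.
- **Reading of results.** A semi-partial R² for practice time of at least .10 is the benchmark for treatment benefit in Models 1-3 and 7. Models 4-6 use McFadden's R² with the same cut-off.
- **What differs by arm.** Section 6 states that "the same HRVB phone coaching offered to regular Lief subscribers will be available to the experimental group participants". The experimental arm alone also has about 30 minutes of rationale and paced-breathing instruction at intake, is encouraged to wear the patch for 8 hours or more a day (Section 3), and receives a $100 equipment-return bonus. Controls complete the momentary surveys and continue their own treatment. No sham device or attention control is described.

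**The concern.** With all controls at zero, part of the spread in practice minutes is simply arm membership. If instruction, coaching, wearing the device or expectancy shifts outcomes, a model that offers practice as its only route for an arm difference will credit some of that shift to minutes. Aim 2 asks what practice does, compares scheduled with in-the-moment practice, and feeds a later R01 trial. A practice result that is partly an arm contrast could lead that trial to be built around practice time when another component did the work.

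**Working it through.** **Inputs from the documents.** Allocation 70:50 (Section 3); N = 100, 5% alpha and 80% power (Aim 2b Power); up to 84 surveys per participant and the .10 benchmark (Section 9). Keeping the allocation ratio at N = 100 gives 100 × 70/120 ≈ 58 and 42.

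**Assumptions, because the documents give no figure.** Mean practice is 50% of target (borrowed from the Aim 1 uptake benchmark), with SD 10-35 percentage points. The arm shift is 0.3, 0.5 or 0.8 SD and acts wholly outside practice. The intraclass correlation is .3-.5, and tests are two-sided.

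**The plan's own figure.** Aim 2b Power gives a detectable R² of .10. With a noncentral F test, λ = N·f² and f² = R²/(1 − R²):
- three terms tested jointly: detectable R² = .102, and power at R² = .10 is 78.9%
- one term: .074; two terms: .091; all eight predictors: .140

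The stated figure therefore fits a joint test of the three practice terms, although the plan does not say so.

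**Closed form, one practice variable.** Let p be the experimental fraction, and m and s the mean and SD of practice in that arm. The share of practice variation that lies between arms is

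w = p(1 − p)m² / [p(1 − p)m² + p·s²].

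With a pure arm shift δ and no effect of minutes, slope × m = w·δ. For p = 70/120 = .583 and m = .50, the term p(1 − p)m² = .0608:
- s = .10: w = .0608/(.0608 + .0058) = .91
- s = .25: w = .0608/(.0608 + .0365) = .625
- s = .35: w = .0608/(.0608 + .0715) = .46

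So 46-91% of the arm shift would be read as practice. Means of 30-70% widen this to 23-95%.

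**Model 7 simulated, no effect of minutes, three practice terms taken jointly.**

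| Arm shift | Significant, 70:50 | Significant, 58:42 | Joint R² ≥ .10, 70:50 | Joint R² ≥ .10, 58:42 |
|---|---|---|---|---|
| 0.3 SD | 20-21% | 16-20% | 5-6% | 7-11% |
| 0.5 SD | 46-56% | 37-50% | 18-27% | 21-31% |
| 0.8 SD | 88-95% | 82-89% | 66-80% | 65-79% |

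Ranges run over the assumed spread of practice. With an arm term added, joint significance is about 5% and the benchmark is met in under 2% at every shift. At 0.5 SD and 70:50, mean joint semi-partial R² falls from .067-.077 to .024, where about .025 is expected with no effect at all. If the benchmark is applied to single terms instead, any one term reaches .10 in about 1-2%, 2-5% and 4-20% of trials at the three shifts (58:42).

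**Linear Models 1-3 simulated** (random intercept, 84 surveys, shift 0.5 SD). When 10-80% of practice variance is between persons, about 2-12% of the shift enters the slope and 7-38% of trials reject. When practice is nearly constant within a person, 18-28% enters and 36-73% reject. An arm term returns rejection to roughly 5%. Logistic Models 4-6 were not simulated.

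**Cost of the arm term.** The between-arm share no longer informs the slope, so its standard error grows by about 1/√(1 − w): 1/√.54 = 1.4 to 1/√.09 = 3.3. With a real dose effect of 0.5 SD at mean practice and no other arm effect, power of the joint test falls from about 55-71% to about 11-32%.

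**The case against.** The best defence is that if benefit runs only through practice, coding controls as 0 is correct and uses valid randomised information; the power loss just shown is then a real price. That stands. It is a reason to keep the 0-coded models and to state the assumption, not to leave the assumption unstated.

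The plan also puts effect sizes ahead of significance and schedules group versions of Models 4-7, so readers would see an arm contrast for substance use beside the practice result. This helps, but a model in which group replaces practice cannot separate the two. The Section 9 introduction alludes to main effects of group in general, yet none is written for Models 1-3, although the Section 2 hypothesis compares negative affect between arms.

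Several stronger readings are tempting, and the documents do not support them:
- **That every arm difference is forced into the practice slope in all seven models.** The slope mixes between-arm and within-arm information, and in Models 1-3 the person intercept absorbs most of a constant shift.
- **That group never sits beside practice.** This is clear for Models 4-6 only; the Model 7 sentence is open.
- **That the plan reports a dose-response.** Its term is treatment benefit. The hypotheses that more practice predicts better outcomes, and the ancillary aim on differing practice times, come close to a dose claim, but the latter is labelled ancillary and post hoc.
- **That the benchmark would often be met by mistake however it is computed.** This needs the joint R². The benchmark wording does not specify joint, and single terms seldom reach .10 at a shift of 0.5 SD.
- **That an arm-adjusted slope would be the causal effect of practice.** Participants choose how much they practise, so motivation could produce a within-arm slope.

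**Conclusion.** The point holds as a cheap improvement. The coding and the missing arm term are plain in the text, as are the non-practice components that only one arm receives. In Model 7 an assumed 0.5 SD shift outside practice would make the practice terms jointly significant in roughly 37-56% of trials instead of about 5%, and meet the joint benchmark in roughly 18-31% instead of under 2%. The problem is smaller in Models 1-3 unless practice hardly varies within persons, and its size in Models 4-6 is unknown. All these sizes rest on assumed arm shifts, practice distributions and intraclass correlations. They show what could happen; they do not show that such an arm effect exists.

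**What to change.** 1. State whether practice stays in Model 7 when group is tested.
2. For Model 7, and likewise for Models 1-6, report the practice slopes with the randomised group indicator in the model, or within the experimental arm only, beside the 0-coded version.
3. Label these slopes as non-randomised associations, and do not read the 0-coded slope alone as an effect of practice minutes.
4. Report the randomised group contrast for Models 1-3 as well.
5. Qualify the power statement in the Section 9 introduction: the gain from coding controls as 0 assumes that the arm acts only through practice time.

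This takes one covariate and some wording, with no change to data collection. The downside is the wider intervals and lower power given above. The arm-adjusted result should therefore stand alongside the 0-coded one and not serve as a pass/fail rule.

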Aim 1. Assess ambulatory HRVB’s uptake by individuals with SUD in terms of practice time, and perceived barriers to uptake based on qualitative participant feedback

We will explore ambulatory HRVB engagement using HRVB practice time (engagement with regular daily practice; engagement with unscheduled, in-the-moment practice). As a general benchmark of intervention uptake success that can be used to guide the subsequent R01 design, we will accept $\geq 50\%$ engagement/adherence to scheduled practice (with consideration given to both number of days practiced, and time practiced each day). In-the-moment practice is harder to assess given we cannot know exactly when participants are experiencing increases/high levels of negative affect outside of each EMA survey, however, as a heuristic, we will accept $\geq 50\%$ in-the-moment practice as indicative of engagement/adherence, based on the ratio of just-in-time practice prompts responded to vs. ignored, and the number of days participants engaged in in-the-moment HRVB practice.

We will also explore perceived barriers to ambulatory HRVB uptake based on qualitative participant feedback provided from the focus groups. Focus group recordings will be transcribed. We will then conduct a systematic qualitative analysis of the transcripts using approaches we have used previously to contextualize findings and offer insights into participants' experiences.

Aim 1 Power

Based on our previous research of a similar nature, we anticipate that engaging 10 participants in focus groups will allow for sufficient diversity of opinion to stimulate discussion and will provide ample time for each participant to share their perspective. We are confident that this sample size will give us the information we need to refine our intervention and research procedures for the subsequent R01.

Aim 2a. Test day-level effects of HRVB practice on affective states and substance use.

We will create indices of EMA recorded positive affect ($[\text{happiness} + \text{calm} + \text{energy}] \div 3$) and negative affect ($[\text{sadness} + \text{guilt} + \text{nervousness} + \text{stress} + \text{craving}] \div 5$) for each EMA survey (2 surveys per day with up to 84 surveys per participant), while also exploring craving scores as a stand-alone measure.

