In Model 6, lagged day-level craving will be added to Model 5. As with the previous model, the dependent variable will be day-level substance use (yes/no), with lagged day-level scheduled and lagged in-the-moment HRVB practice combined (with controls' HRVB practice coded as 0), lagged day-level negative affect, lagged day-level craving, and the lagged HRVB practice \times lagged craving interaction term as the independent variables, controlling for age, sex, nicotine use (yes/no), medications known to affect the cardiovascular system (yes/no), and baseline past-month AOD use (percent days abstinent). We will also test this model with group as independent variable instead of HRVB practice.

We anticipate that greater HRVB practice and lower negative affect and craving will be associated with lower probability of substance use at the subsequent EMA survey, and that the HRVB practice \times negative affect/craving interaction terms will indicate that HRVB practice mitigates the deleterious relationship between negative affect and craving, and subsequent substance use. McFadden's $R^2 \geq .10$ (medium effect size) will be our benchmark for preliminary demonstration of day-level treatment benefit.

Models 4-6

Substance use = *day-level scheduled HRVB practice_{t-1} + day-level in-the-moment HRVB practice_{t-1} + [day-level scheduled HRVB practice_{t-1} * day-*

level in-the-moment HRVB practice_{t-1}] + age + sex + nicotine use + medications known to affect the cardiovascular system + baseline past-month AOD use + error

Substance use = *total day-level HRVB practice_{t-1} + day-level negative affect_{t-1} + [total day-level HRVB practice_{t-1} * day-level negative affect_{t-1}] + age + sex + nicotine use + medications known to affect the cardiovascular system + baseline past-month AOD use + error*

Substance use = *total day-level HRVB practice_{t-1} + day-level negative affect_{t-1} + day-level craving_{t-1} + [total day-level HRVB practice_{t-1} * day-level negative affect_{t-1}] + [total day-level HRVB practice_{t-1} * day-level craving_{t-1}] + age + sex + nicotine use + medications known to affect the cardiovascular system + baseline past-month AOD use + error*

Aim 2a Power

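### Craving sits inside the negative affect index and beside it in Model 6, so a craving coefficient of zero means equal weight with the other items, not no effect

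*Combined protocol and SAP*

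**What the plan says.** All of this is in Section 9, Statistical Analysis. The opening paragraph says that, because power is limited, "we will focus on interpreting effect sizes to inform a subsequent R01 trial".

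Aim 2a builds negative affect as the mean of sadness, guilt, nervousness, stress and craving; the formula ends "stress} + \text{craving}] \div 5$) for each EMA survey". The same sentence adds "while also exploring craving scores as a stand-alone measure". No second craving item and no craving-free index is described.

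The purpose of Models 5 and 6 is given as "while also testing whether HRVB decouples the anticipated relationship of day-level negative affect" (Model 5) and of craving (Model 6) with later substance use. For Model 6 the text says "In Model 6, lagged day-level craving will be added to Model 5". Its list of predictors then names negative affect, craving and one interaction, practice by craving: "lagged craving interaction term as the independent variables". The printed Model 6 equation has that interaction and practice by negative affect as well. The sentence on expected results speaks of interaction terms in the plural and expects mitigation for both negative affect and craving.

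Likelihood ratio tests will compare nested models through "the difference in -2 log-likelihood statistics between pairs of base and expanded models". The pairs are not named. Models 5 and 6 are also to be run with group in place of practice.

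**The concern.** The plan treats negative affect and craving as two predictors, each with its own effect on use and its own decoupling question. In Model 6 they share an item. When a composite and one of its components stand in the same linear predictor, the component's coefficient measures how far its weight departs from the weight that the composite already gives it. A reader who takes a null or negative Model 6 craving coefficient at face value could conclude that craving does not matter, or protects, when neither is true. In a pilot that reports effect sizes for a later trial, the meaning of a coefficient matters more than its p-value.

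**Working it through.** **Inputs.** The five-item index, the Model 5 and 6 equations, the Model 6 text list, and the Aim 2a power figures are from Section 9. Assumed: the stand-alone craving score is the same EMA item as in the index, and both are used raw or centred the same way.

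**1. The plan's own figure.** The only figure that covers Model 6 is power above 99% for the practice main effect. 100 × 42 × 2 = 8,400 reports (the plan says 8,300). With r = 0.15 and two-sided 5% alpha, Φ(atanh(0.15)·√(8,300 − 3) − 1.96) is 1.00, so it reproduces under the plan's assumption of conditional independence. It says nothing about craving.

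**2. Craving main effect.** Let NA5 be the planned index, NA4 = (sadness + guilt + nervousness + stress)/4, and C = craving. Then NA5 = 0.8·NA4 + 0.2·C, and

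b5·NA5 + c·C = 0.8·b5·NA4 + (c + 0.2·b5)·C.

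So b4 = 0.8·b5 and c4 = c + 0.2·b5, which gives c = c4 − b4/4. This holds for the text list and for the equation. A random intercept does not alter it. With an illustrative b4 of 0.40:

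| True craving effect c4 | Model 6 coefficient c |
|---|---|
| 0 | 0 − 0.10 = -0.10 |
| 0.10 | 0.10 − 0.10 = 0.00 |
| 0.40 | 0.40 − 0.10 = 0.30 |

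**3. Practice by craving.** Let d4 and e4 be the practice-by-NA4 and practice-by-craving effects, and e the printed practice-by-craving coefficient.

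- Equation (both interactions): the same algebra gives e = e4 − d4/4. With d4 = -0.20, an e4 of -0.05 appears as 0.00 and an e4 of 0 appears as +0.05. With d4 = 0 nothing shifts.
- Text list (practice by craving only): e is the same under either index.

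One simulated data set of 400,000 records (inter-item correlation 0.4, every item decoupled equally) shows both. Under the equation the estimate is -0.030 with five items and -0.072 with four; the estimated d4 is -0.168, and -0.072 + 0.168/4 = -0.030. Under the text list it is -0.139 with either index.

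**4. Model 5 versus Model 6.** This is the natural likelihood ratio pair. Under the equation it has 2 df, and its null with the five-item index is c4 = b4/4 and e4 = d4/4, that is, equal weighting. Under the text list Model 6 lacks practice by negative affect, so Model 5 is not nested in it and the test is not available.

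**5. Illustrative rejection rates for that test.** Assumed: equation form, 5% use, inter-item correlation 0.3, no practice effects, 100 people × 83 surveys, random intercept SD 1, about 400 simulations per row (error about 4 points at 17%).

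| b4 | c4 | Five items | Four items |
|---|---|---|---|
| 0.40 | 0 | 17% | 6% |
| 0.40 | 0.10 | 5% | 23% |
| 0.80 | 0 | 51% | 6% |

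Treating 8,300 records as fully independent, which is more than the plan claims, the first row is 24% against 5%. On the same basis a craving effect of 0.40 is detected in 98% against 100%.

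**6. What does not change.** The two codings of Model 6 span the same predictors. Log-likelihood, McFadden R² and the practice main effect are identical. Since b5 = 1.25·b4 (and d5 = 1.25·d4 under the equation), so are the z values of the negative affect terms.

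**The case against.** The strongest reply is that Model 6 is only reparameterised. Its fit and its benchmarked R² stand, and craving's own effect can be recovered from the same fit as c + b5/5. That is right, but the standard error of that sum needs the coefficient covariance, no such step is planned, and Model 5 with five items is not equivalent to Model 5 with four.

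A second reply is that the rejection rates are peripheral. This largely stands. The plan puts effect sizes ahead of significance, names no test pairs, and expects craving to have an effect, whereas the largest rates assume that it has none. Nor is 17% a false-positive rate of the test as specified: it is power against a null of equal weighting that is then false. If the lag uses only same-day survey pairs, about half the records, the independent-record 24% falls to about 14%.

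A reader might infer three stronger things that the documents do not support:

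- That the craving decoupling term is distorted in any case. It shifts only under the equation, and only if practice by four-item negative affect is not zero.
- That Model 6 fails through collinearity. For inter-item correlations of 0 to 0.5 the variance inflation factor is only 1.25 to 2.5; the problem is what the coefficient means.
- That the next trial's target would be chosen wrongly. The plan says that effect sizes will inform that trial, not that this coefficient will decide its target.

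**Conclusion.** The point holds for the Model 6 craving main effect under either form of the model: it is low by exactly one quarter of the four-item negative affect effect. This is algebra and rests only on the same item being used twice and scored the same way. For practice by craving, and for the Model 5 versus Model 6 test, it holds under the printed equation only. There, if negative affect is decoupled as the plan expects, the shift works against seeing craving decoupled. The mismatch between text and equation is therefore part of the point, because it decides how far the problem reaches. The group versions behave in the same way.

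The sizes quoted depend on assumed effects, use rate and correlations. Large craving effects would still be found. The plan should be changed, but the issue is confined to reading Models 5 and 6 and does not undermine the practice main effect or the Model 6 benchmark.

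**What to change.** - In Models 5 and 6 and their group versions, define negative affect as (sadness + guilt + nervousness + stress)/4 and enter craving only as its own predictor in Model 6. Report the five-item index as a sensitivity analysis.
- Reconcile the Model 6 text with its equation so that both practice interactions are included and Model 5 is nested in Model 6.
- Name the model pairs for the likelihood ratio tests.

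This takes a few lines, needs no new data, and leaves Models 1 to 4 and 7 as planned. The costs are:

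- **Reliability.** With equal inter-item correlation r (assumed), alpha = k·r/(1 + (k − 1)·r) falls from 0.68 to 0.63 at r = 0.3 and from 0.83 to 0.80 at r = 0.5.
- **Benchmark.** Model 5's McFadden R² can be lower against the .10 benchmark when craving matters, for example 0.033 to 0.024 at an assumed craving effect of 0.40.
- **Consistency.** Negative affect would have five items in Model 1 and four in Models 5 and 6; a four-item version of Model 1 could be added as a sensitivity analysis.

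The change removes the overlap due to construction, not the real correlation. If only craving mattered, the four-item Model 5 term would still carry 4r/(1 + 3r) of its effect, which is 63% at r = 0.3 and 80% at r = 0.5. The report should say so.
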